11 INTERIM ANALYSES

No formal interim analysis will be performed for determining whether to stop (or modify) the study early (i.e., no hypothesis testing will be conducted *ad interim*). Therefore, no adjustment for multiple testing is required. This study includes an IDMC and ISB that will assess safety of ACT-541468 on a regular basis as per the IDMC and ISB charters, respectively. Safety and efficacy data supporting the review by the IDMC will be provided by Idorsia for the part of analyses that are blinded and by an ISAC for the unblinded part.

12 GENERAL DEFINITIONS AND DERIVATIONS

12.1 Treatment start and end dates

Run-in single-blind placebo treatment start or end date is the earliest or latest, respectively, date of dose intake recorded on the 'Study Single-Blind (Run-In) Treatment Log' page.

DB study treatment start or end date is the earliest or latest, respectively, date of dose intake recorded on the 'Study Double Blind Treatment Log' page.

Run-out single-blind placebo treatment start and end date is the earliest and latest date of dose intake recorded on the 'Study Single-Blind (Run-Out) Treatment Log' page.

12.2 Study periods

The Screening period is defined as the time from the informed consent date until one day before the Run-in period start date.

The Run-in period is defined as the time from the start of the run-in single-blind placebo treatment to one day before start of DB study treatment or, for those not starting DB study treatment, to run-in single-blind placebo treatment end date.

The DB study period is defined as the time from the day of DB study treatment start until the day of EODBT (Visit 8, 2nd morning), or, for those who prematurely discontinued DB study treatment (i.e., those without an EODBT date), until one day after DB study treatment end date (if the treatment is taken before midnight) or the day of DB study treatment end date (if the treatment is taken after midnight). Time of treatment intake between 00:00 and 11:59 is considered as 'after midnight', while a time between 12:00 and 23:59 is considered as 'before midnight'. For any missing or incomplete time, it is presumed that the treatment was taken before midnight. For subjects who complete DB study treatment with an

interruption before continuing the run-out single-blind placebo treatment, the end of DB study period is the run-out single-blind placebo treatment start date – 1 day.

For those subjects in the TWS, the treatment withdrawal period (or Run-out period) is defined as the time from one day after the end of the DB study period to the latter of seven days after the end of the DB study period or Visit 10 date.

The safety follow-up period is defined as the time from one day after the end of the treatment withdrawal period for those starting the treatment withdrawal period (i.e., subjects in the TWS) until EOS date; or from one day after the end of the DB study period for those not starting the treatment withdrawal period until EOS date.

12.3 Treatment day and Study day

The Treatment day for an assessment or event will be calculated using the DB study treatment start date as reference.

For assessments/events occurring on or after the start date of DB study treatment, Treatment day will be positive and will be calculated as:

Treatment day (days) = Date of assessment/event – Start date of DB study treatment + 1 day

The first day of DB study treatment is Treatment day 1.

For all assessment/events occurring prior to the start date of DB study treatment, Treatment day will be negative and will be calculated as:

Treatment day (days) = Date of assessment/event – Start date of DB study treatment

The Study day for an assessment or event will be calculated using the randomization date as reference.

For assessments/events occurring on or after the randomization date, Study day will be positive and will be calculated as:

Study day (days) = Date of assessment/event – randomization date + 1 day

The day of randomization date is Study day 1.

For all assessment/events occurring prior to the randomization date, Study day will be negative and will be calculated as:

Study day (days) = Date of assessment/event – randomization date

Treatment day and/or Study day will be displayed in the data listings as appropriate.

12.4 Baseline

Baseline is the last non-missing assessment performed or value measured before or on the day of first dose of DB study treatment, unless otherwise defined in the specific analysis section.

An assessment done on the day of the DB study treatment start date is considered a baseline assessment and is not considered a post-baseline assessment in the DB study period.

Subjects with no data on a particular parameter before the first treatment administration will have a missing baseline (and change from baseline) for this parameter.

12.5 Change from baseline

The change from baseline is defined as post-baseline value (any assessment performed after baseline and up to EOS) minus baseline value. A positive number indicates an increase as compared to baseline.

12.6 Handling of data when total sleep time is zero

If the TST is recorded as zero (i.e., subject did not fall asleep during the night), then:

- WASO is set as missing since subject is never at risk, and
- LPS is set as 480 minutes which is equal to the duration of time in bed.

If the sTST is recorded as zero, then similarly:

- sWASO is set as missing, and
- sLSO is set as 480 minutes.

12.7 Missing data patterns

Monotone missing data pattern: Given a dataset with variables, Y_1, Y_2, \dots, Y_t (in that order) and V_j is missing for a particular subject, then all subsequent variables $V_k, k > j$, are missing for that subject. In addition, given the same dataset and V_j is observed for a particular subject, then all previous variables $V_k, k < j$, are also observed for that subject. Monotone missing data patterns are typically encountered when a subject prematurely withdraws from a study and is expected to be more likely seen than non-monotone missing data patterns.

In the examples below, an 'X' indicates that the variable is observed in the corresponding group and a '.' means that the variable is missing.

Example of monotone missing data patterns:

Subject	Y1	Y2	Y3
1	X	X	X
2	X	X	.
3	X	.	.

When missing data are non-monotone, data can also be missing at intermediate visits (i.e., missing a given visit, but observed again at the next visit). Non-monotone missing data patterns are commonly turned into monotone missing data patterns using MI (based on MCMC), which are then subsequently analyzed using MI methods based on monotone missing data.

Example of non-monotone missing data patterns:

Subject	Y1	Y2	Y3
1	X	X	X
2	.	X	X
3	.	.	X
4	.	X	.
5	X	.	X

12.8 Time window definitions for calculating subjective endpoints

The meaning of the first PSG end date and the last PSG end date at a given visit (Visit 3, Visit 6 and Visit 8) are shown in [Table 6](#).

Table 6 Meaning of the first and last PSG end date at Visits 3, 6 and 8

Visit 3, Visit 6 and Visit 8			
First PSG		Last PSG	
Start date (evening)	End date (morning)	Start date (evening)	End date (morning)

Values falling in the following time windows will be used to calculate weekly averages for the subjective endpoints; values from PSG night will not be included:

Screening: the 7 consecutive days immediately preceding the Run-in single-blind placebo treatment start date but after PSG end date at Visit 1 (morning) (i.e., 7-day window = [Max. (Run-in single-blind placebo treatment start date – 7 days; PSG end date at Visit 1 [morning]); Run-in single-blind placebo treatment start date – 1 day]).

Baseline (Run-in period): the 7 consecutive days immediately preceding the first PSG at Visit 3, but after Run-in single-blind placebo treatment start date (i.e., 7-day window = [Max. (End date of first PSG at Visit 3 – 7 days; Run-in single-blind placebo treatment start date); End date of first PSG at Visit 3 – 1 day]). The time window for Baseline may be less than 7 days. Baseline will be missing for any subjects without a PSG at Visit 3.

Month 1: the 7 consecutive days immediately preceding the first PSG at Visit 6 (i.e., 7-day window = [End date of first PSG at Visit 6 – 7 days; End date of first PSG at Visit 6 – 1 day]). For subjects missing PSG at Visit 6, the 7-day window = [Study day 23; Study day 29].

Month 3: the 7 consecutive days immediately preceding the first PSG morning at (Visit 8 i.e., 7-day window = [End date of first PSG at Visit 8 – 7 days; End date of first PSG at

Visit 8 – 1 day]). For subjects missing PSG at Visit 8, the 7-day window = [Study day 79; Study day 85].

Run-out: the 7 consecutive days immediately following the PSG morning at Visit 9 (i.e., 7-day window = [Date of PSG morning at Visit 9 + 1 day; Min. (Date of PSG morning at Visit 9 + 7 days; Visit 10 date)]). For subjects missing PSG at V9, the 7-day window = [Treatment withdrawal period start date; Min. (Treatment withdrawal period start date + 6 days; Visit 10 date)].

Table 7 defines the time windows used to calculate weekly averages for certain subjective measures that will be summarized per week. These subjective measures include sTST, sWASO, sLSO and IDSIQ scores (i.e., Total score; Alert/Cognition, Mood and Sleepiness domain scores).

Table 7 Time windows (in days) to calculate weekly averages for certain subjective endpoints

Week	Study day (7-day window)
1	2–8
2	9–15
3	16–22
4*	23–29
5	30–36
6	37–43
7	44–50
8	51–57
9	58–64
10	65–71
11	72–78
12*	79–85

* These days might not be the same as in the definition above (Month 1, Month 3).
Values from PSG nights and Run-out period will not be included.

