3.1.1.3 Safety follow-up phase

The **safety follow-up phase** starts after EODBT. It consists of a single-blind placebo Run-out period of 7 days and a Safety follow-up period.

The **Run-out period** starts in the evening of Visit 9. Visit 9 consists of one PSG night on single-blind placebo treatment. Visit 9 is followed by 6 days at home with single-blind placebo treatment. The eDiary is completed every day during the Run-out period. The end of the Run-out period (End-of-Treatment [EOT]) is reached after all visit assessments have been performed at Visit 10.

The **Safety follow-up period** starts after EOT and ends 30 days after last dose of DB study treatment intake for subjects that are not enrolled in the ID-078A303 extension study.

Subjects who complete DB study treatment and the Run-out period are eligible to enter the ID-078A303 extension study (if approved by the national health authorities and local Independent Ethics Committees / Institutional Review Boards [IECs/IRBs]). For these subjects, the Safety follow-up period ends at the date of enrolment into ID-078A303.

[figure not shown]
End-of-Study (EOS) for an individual subject is defined as the date of the 30-day follow-up telephone call (Visit 11, Day 115) or the date of enrollment into the ID-078A303 extension study. If a subject is prematurely discontinued from study treatment, EOS is performed as planned on Day 115. If a subject withdraws consent and does not wish to

participate in the study any longer, EOS is the date of consent withdrawal for this subject. If a subject is declared lost to follow-up, EOS is the date of last successful contact for this subject.

The visit schedule and protocol-mandated procedures are performed according to the table of assessments [Table 1] and are described in Section 7.

The overall study design is depicted in [Figure 1].

Figure 1 Study design

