One PSG night is planned after the first day of treatment discontinuation and the sleep diary completed in the 3 days following treatment discontinuation will allow assessment of rebound insomnia on objective and subjective parameters, respectively. Thus, this 7-day run-out period allows to capture long-term withdrawal effects, as well as shorter-term potential rebound symptoms.

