6.5 Safety endpoints

In addition to the standardized collection of AEs, safety data specific to insomnia and its treatment will be assessed as follows:

- Withdrawal effects (physical dependence) upon treatment discontinuation will be assessed based on the changes from last assessment on DB treatment (Visit 8, 2nd morning) to run-out period in the BWSQ total score (Visit 9 and Visit 10), the occurrence of relevant AEs and marked ECG abnormalities.
- Rebound insomnia will be assessed based on objective sleep parameters (WASO, LPS and TST) at Visit 9 as compared to Visit 3. It will also be assessed using subjective sleep parameters (sWASO, sLSO and sTST) from run-out period as compared to baseline.
- Next-day residual effect will be assessed based on changes from baseline (Visit 3) to Month 1 and Month 3 in:
 - Coding sub-test[©]
 - SDS[©]
 - Scores on the VAS (mm)
- SAEs up to 30 days after DB study treatment discontinuation or until enrollment into the extension study.
- TEAEs up to 30 days after DB study treatment discontinuation or until enrollment into the extension study.

- AEs leading to premature discontinuation of the DB study treatment.
- AEs of special interest after adjudication by ISB:
 - narcolepsy-like symptoms (i.e., EDS, cataplexy and complex sleep behavior events including hallucinations/sleep paralysis)
 - suicide/self-injury
- Change from baseline (Visit 3) to Month 1 (Visit 6) and Month 3 (Visit 8) in vital signs (mean of the 2 PSG nights in systolic and diastolic blood pressure [BP] and pulse rate).
- Change from baseline (Visit 1) to Month 3 (Visit 8) in body weight.
- Marked ECG abnormalities on DB study treatment.
- Change from baseline (Visit 3) to Month 3 (Visit 8) and the end of the run-out period (Visit 10) in ECG parameters.
- Marked laboratory abnormalities on DB study treatment.
- Change from baseline (Visit 3) to Month 1 (Visit 6) and Month 3 (Visit 8) in laboratory parameters.
- Occurrence of suicidal ideation and/or behavior on DB study treatment based on C-SSRS[®].

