The changes from baseline to the treatment withdrawal period (Visit 9, run-out) in objective sleep parameters (WASO, LPS and TST) will be summarized using descriptive statistics.

The changes from baseline (mean value based on the screening sleep diary entries performed at home in the 7 days immediately preceding the first PSG at Visit 3) to the treatment withdrawal period (after PSG night at Visit 9) in subjective sleep parameters (sWASO, sLSO, and sTST) will be summarized using descriptive statistics.

Next-day residual effect

Observed values and changes from baseline to Month 1 and Month 3 in Coding sub-test[®], SDS[®], and VAS scores (mm) assessing morning sleepiness, daytime alertness and daytime ability to function, will be summarized.

C-SSRS[®]

Number (%) of subjects with suicidal ideation, suicidal behavior, and/or self-injurious behavior without suicidal intent based on the C-SSRS[®] during DB treatment will be tabulated.

Shifts from baseline showing any changes in suicidal ideation and suicidal behavior during DB treatment will also be provided. Subjects will be summarized under the worst of the following three categories, shown here in the order from best to worst: 1) No suicidal ideation or behavior, 2) Suicidal ideation only, and 3) Suicidal ideation and behavior.

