7.7 Rebound insomnia

The TWS will be used to assess the potential for rebound insomnia. The change from baseline (Visit 3) to the treatment withdrawal period (Visit 9, run-out) in objective sleep parameters (WASO and LPS) will be summarized. The change from baseline (mean value based on the screening sleep diary entries performed at home in the 7 days immediately preceding the first PSG at Visit 3) to the treatment withdrawal period (after PSG night at Visit 9 [see Section 12.8]) in the subjective sleep parameter sTST will be summarized. Empirical cumulative distribution function plots of these objective and subjective sleep parameters for each treatment group will be provided, together with a summary showing the cumulative number and percentage of subjects meeting a certain threshold for the observed range of values.

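### Subjective rebound rests on one sTST average over 6–7 home entries; no planned diary summary isolates the nights just after the Visit 9 PSG

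*SAP*

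**What the plan says.** Protocol 3.2.1, explaining the run-out, plans one PSG night after the first day off drug and adds that "the sleep diary completed in the 3 days following treatment discontinuation will allow assessment of rebound insomnia" on the subjective side. The next sentence separates two time scales: "this 7-day run-out period allows to capture long-term withdrawal effects, as well as shorter-term potential rebound symptoms". It does not say whether the Visit 9 night counts as one of the 3 days.

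The endpoint and analysis sections name no 3-day window. Protocol 6.5 assesses "subjective sleep parameters (sWASO, sLSO and sTST) from run-out period as compared to baseline". Protocol 10.3.3 places the subjective comparison in the withdrawal period after the Visit 9 PSG night. Protocol 3.1.1.3 gives the length: "Visit 9 is followed by 6 days at home with single-blind placebo treatment".

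SAP 7.7 summarises WASO and LPS at Visit 9. For the diary, the change from baseline "in the subjective sleep parameter sTST will be summarized". It also plans "Empirical cumulative distribution function plots of these objective and subjective sleep parameters", with threshold tables of the same values. SAP 12.8 sets the window: "Run-out: the 7 consecutive days immediately following the PSG morning at Visit 9". Its formula starts one day after that morning, stops at the earlier of 7 days or Visit 10, and leaves out PSG-night values. For subjects without a Visit 9 PSG, the window starts at the beginning of the treatment withdrawal period. SAP 10.1 accepts any 2 entries as enough for a weekly mean.

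**The concern.** Rebound insomnia is a named safety endpoint, and the protocol itself describes it as the shorter-term effect. A sleep loss that fades within a few nights is averaged with later, recovered nights, so it reads smaller than it was. For a safety question, that error is in the reassuring direction.

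No other planned summary fills the gap:

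- WASO and LPS at Visit 9 describe night 1 only.
- The distribution plots and threshold tables in SAP 7.7 use the same averaged sTST.
- The weekly summaries in SAP Table 7 exclude the run-out.
- Night-time PGI-S and PGI-C are collected at Visit 10, but they recall 7 nights, and SAP 6.3 summarises them only to Month 1 and Month 3.
- BWSQ, ESS and withdrawal-period adverse events are summarised, but none measures sleep night by night. Listings give no group estimate.

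From night 2 on, diary sTST is therefore the only sleep measure summarised for rebound, and each subject contributes a single average.

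**Working it through.** **Inputs.** Target days from protocol Table 1: last double-blind PSG night 84/85, Visit 9 PSG night 85/86, Visit 10 on Day 92 (+ 2 days). Window formula from SAP 12.8. The sTST item asks about the previous night (SAP 6.1.2), so the entry on morning *d* reports off-drug night *d* − 85.

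**Entries in the window.** The Visit 9 PSG morning is Day 86, so the window is [Day 87; min(Day 93, Visit 10)].

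- Visit 10 on Day 92: Days 87–92, 6 entries, nights 2–7. This matches the 6 home days in protocol 3.1.1.3.
- Visit 10 on Day 93 or 94: Days 87–93, 7 entries, nights 2–8.
- Visit 9 PSG missing: Days 86–92, 7 entries, nights 1–7. Night 1 enters, but the result is still one average.

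**Dilution.** Assume a complete diary and a constant sTST loss from night 1 to night E. The comparator is the mean over the first 3 home mornings, Days 87–89 (nights 2–4).

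Ratio = (affected nights in SAP window ÷ 6 or 7) ÷ (affected nights among 2–4 ÷ 3).

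**Precision.** With independent nights of equal variance, the SD ratio of a 3-entry to a 6-entry mean is √(6/3) = 1.41. For change from a 7-entry baseline around a stable subject level, it is √[(1/3 + 1/7)/(1/6 + 1/7)] = 1.24. With night-to-night correlation r, the first ratio becomes √[2(1 + 2r)/(1 + 5r)], which is 1.07 at an assumed r = 0.5. Relative signal-to-noise of the 3-entry mean against the 6-entry mean is (1 ÷ the 6-entry ratio) ÷ SD ratio.

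| E | Ratio, 6 entries | Ratio, 7 entries | Signal-to-noise (SD ratio 1.41 / 1.24) |
|---|---|---|---|
| 2 | (1/6)/(1/3) = 0.50 | (1/7)/(1/3) = 0.43 | 1.41 / 1.61 |
| 3 | (2/6)/(2/3) = 0.50 | (2/7)/(2/3) = 0.43 | 1.41 / 1.61 |
| 4 | (3/6)/(3/3) = 0.50 | (3/7)/(3/3) = 0.43 | 1.41 / 1.61 |
| 5 | (4/6)/1 = 0.67 | (4/7)/1 = 0.57 | 1.06 / 1.21 |
| 6 | (5/6)/1 = 0.83 | (5/7)/1 = 0.71 | 0.85 / 0.97 |
| 7 | (6/6)/1 = 1.00 | (6/7)/1 = 0.86 | 0.71 / 0.81 |

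E = 1 is left out because neither home mean contains it; only Visit 9 shows it.

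The result does not depend on a sharp cut-off. If the loss halves each night, the SAP mean is 0.164 (6 entries) or 0.142 (7) of the night-1 loss. The nights 2–4 mean is 0.292, so the ratios are 0.56 and 0.49.

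**In minutes.** Take an assumed loss of 30 min on nights 1–3. The SAP mean shows 30 × 2/6 = 10 min, or 30 × 2/7 ≈ 9 min. The nights 2–4 mean shows 30 × 2/3 = 20 min.

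**Two-entry rule.** There are 15 ways to keep 2 of 6 entries, and 3 of them fall wholly in nights 5–7. This counts what the rule permits. It does not predict how often it will happen.

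**The case against.** The strongest reply is that the SAP does what the protocol's endpoint and analysis sections ask, and that stands. Protocol 6.5 and 10.3.3 give the run-out after the Visit 9 PSG night, and SAP 7.7 and 12.8 implement it. The 3-day phrase sits only in the rationale, where it says what the diary will allow and does not define a window. A reader might infer that the SAP contradicts the protocol or changes the window without declaring it. The documents do not support that: the 3 days lie inside the run-out, however they are counted.

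A reader might also infer that the first night off drug is never summarised. It is, through WASO and LPS at Visit 9, and the fallback window can bring night 1 into the diary average.

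The size rests on assumed profiles, which is also true. Comparing the SAP average with a nights 1–3 mean would give starker ratios. However, it would mix a sleep-laboratory entry with a home-only baseline, so that comparison is not used here.

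Finally, a full week mirrors the 7-day baseline and is the more precise summary if rebound lasts 6 or 7 nights. That argues for keeping it. It does not argue against adding an early-night summary beside it.

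**Conclusion.** The point holds as a gap in a descriptive safety summary. The plan has no diary summary for the nights just after Visit 9, which protocol 3.2.1 singles out. Under a constant loss ending on night 2, 3 or 4, the planned average shows about half (0.50) or somewhat less (0.43) of the nights 2–4 mean. The understatement shrinks as rebound lasts longer: little or nothing is lost when it fills the run-out. These figures assume visits on target days, a Visit 9 PSG, a complete diary and a constant loss. The documents give neither a duration nor a shape for rebound, so the ratios show sensitivity and are not a forecast.

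No hypothesis test, alpha allocation, or primary or secondary conclusion is affected. The change is worth making because a short rebound is the kind the current average shows least well, and the remedy needs no new data.

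**What to change.** Keep the full run-out sTST average in SAP 7.7 and 12.8. Beside it, add one of the following:

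- the change from baseline in sTST by individual run-out day; or
- the change from baseline over the first 3 home mornings after the Visit 9 PSG (Days 87–89 on target), requiring at least 2 entries as in SAP 10.1.

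Show the Visit 9 morning entry separately, since baseline uses home entries only and SAP 12.8 excludes PSG-night values. Record this in SAP Section 13 as an additional rebound summary that addresses protocol 3.2.1. No correction to the protocol is needed.

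The cost is SAP wording and a few summary columns; the diary is already completed daily to Visit 10. The statistical cost is noise: the SD of a 3-entry mean is up to 1.41 times that of the 6-entry mean, or 1.24 times for change from baseline, assuming independent nights. Signal-to-noise improves for a loss ending on nights 2 to 5. It falls for one ending on night 6 or 7, by up to 29% (or 19% for change from baseline). Hence the short summary should stand beside the full average and not replace it.
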